3.2. Secondary Endpoint(s)

Secondary endpoints evaluated during the entire double-blind period include:

- Daily OFF time (hours): change from baseline in average daily OFF time by Visit.
- Daily ON time with troublesome dyskinesia (hours): change from baseline in average daily ON time with troublesome dyskinesia by Visit.
- Daily ON time without troublesome dyskinesia (hours): the change from baseline in average daily ON time without troublesome dyskinesia (i.e. without dyskinesia or with non-troublesome dyskinesia, or alternatively “good time”) by Visit.

The same algorithm and rules employed for the calculation of OFF time will be used for the secondary variables. Baseline is defined using the 3 Hauser diary days prior to Day 0.

- MDS – Unified Parkinson’s Disease Rating Scale (MDS-UPDRS) Part III: Change from Baseline in MDS-UPDRS Part III Score by Visit.
- MDS-UPDRS Parts I, II, IV, and total score: Change from Baseline in the MDS-UPDRS Parts I, II, IV and Total Scores by visit.

The MDS-UPDRS will be collected at times specified in the STUDY PROCEDURES section of this protocol. *Although not required, every effort should be made to have the same individual perform the ratings for an individual subject throughout the course of the study.*

MDS-UPDRS Part III should be assessed consistently and approximately 2 to 4 hours following L-Dopa dose (except at screening).

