### 2.2. Secondary Objectives

- To evaluate the dose-response on motor symptoms of PF-06649751 administered once daily in subjects with Parkinson's disease.
- To evaluate the safety and tolerability of PF-06649751 administered once daily in subjects with Parkinson's disease.
- To evaluate the effect of PF-06649751 administered once daily on dyskinesia in subjects with Parkinson's disease.

CCI

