### **5.9. Rescue Medication**

Rescue medication is permitted in the form of L-Dopa. The dose and dose frequency can be defined using investigator discretion based on patients' needs. Rescue L-Dopa may be administered if needed in between study visits based on a phone consultation and the discretion of the investigator.

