An average daily OFF time (using 3 days recording the Hauser diary prior to the visit) will be calculated at all time points for each subject, which includes Baseline (prior to Day 0), Week 3, Week 5 and Week 10 (End of Period A), Week 13 (Period B; exists prior to Protocol Amendment 2 only) and also Week 15 (End of Period B). Change from baseline will then be calculated. Week 10 is the primary endpoint.

- Week 3 Hauser home diary data will be collected at the Week 3 visit for subjects randomized prior to Protocol Amendment 2, and at the Week 3 visit for subjects randomized under Protocol Amendment 2, where sites choose to perform an in-clinic visit (instead of a phone visit).
- Week 3 Hauser home diary data will be collected at Week 4 for subjects randomized under Protocol Amendment 2, when sites perform a phone visit for Week 3. The Week 3 phone visit will be used as the nominal visit.

In calculating the average daily OFF time, the following algorithms and rules are applied. (Rescue medication methods below are for all periods through Period A, and additionally Period B for subjects consented under Protocol Amendment 2 prior to entering Period B).

Valid Hauser Diary Days

1. Subjects who do not complete at least 12 awake hours of symptom diary data (not including ASLEEP time) will have that daily data set to missing (i.e. will not be considered as a valid symptom diary day). There will be no imputation of data for these diary days.
2. Any Hauser diary day on which rescue medication was used will NOT be considered a valid symptom diary day. The Hauser diary data reported on that day hereafter referred to as a rescue diary day, will not be used. As described more completely in the instruction for daily OFF time below, baseline data will be used to impute the observed response on these days. (All periods through Period A, and additionally Period B for subjects consented under Protocol Amendment 2 prior to entering Period B).

Entries at 30-minute Intervals (Only for subjects who have ≥ 12 awake hours of Hauser home diary data)

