7. The daily OFF time for every rescue diary day will be replaced by the subject's baseline OFF time, that is, the baseline 3-day average. (All periods through Period A, and additionally Period B for subjects consented under Protocol Amendment 2 prior to entering Period B).

Daily Average (Rescue diary days are for all periods through Period A, and additionally Period B for subjects consented under Protocol Amendment 2 prior to entering Period B)

8. Valid home diary days (at least 12 awake hours, after all imputation) and/or rescue diary days will be used to compute the average daily OFF time. The valid home or rescue diary day must be within 7 days of the clinic visit (or phone visit for Week 3 only as noted below or assigned to the closest planned visit as noted below) but not on or after the day of the clinic visit. If more than 3 valid home or rescue diary days are available, the 3 days closest to the clinic visit will be used.
 - Prior to Protocol Amendment 2, the three consecutive days before Day 0 could occur anytime during the screening period and was not restricted to within a week of the visit. Therefore, all home diaries before Day 0 will be considered for Baseline, with the 3 days closest to Day 0 being used for analysis.
 - Subjects, who have a phone visit for Week 3 and their home diary collected at Week 4, will use their Week 3 phone visit to determine within 7 days.
 - If a valid home or rescue diary is considered for exclusion based on the "within 7 days" rule, it will still be included if its nominal visit is equal to the closest planned visit, otherwise it will be excluded. Planned visits: Baseline (Day -1), Week 3 (Day 21), Week 5 (Day 35) or Week 10 (Day 70).
 - i. Example 1: A subject who completed Week 3 diaries on Days 8, 9, and 10 with the actual Week 3 visit occurring on Day 21. All diaries excluded as all Week 3 diaries would all have been closer to Baseline (Day -1) than Week 3 (Day 21).

- ii. Example 2: A subject who completed Week 10 diaries on Days 61, 62 and 63 with the actual Week 10 visit occurring on Day 70. All diaries included because the diaries are closest to Day 70 which matches the clinic visit (Week 10).
 - iii. Example 3: A subject who completed their Week 3 diaries on Days 11, 12 and 13 but the actual Day 21 visit occurred on Day 24. All diaries included because the diaries are closest to Day 21 which matches the clinic visit (Week 3).

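### Baseline substitution on rescue days, extended to ON time with troublesome dyskinesia, erases any worsening recorded on those days, and no planned analysis shows the recorded values

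*SAP*

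**What the plan says.** SAP 3.1 builds the rule for OFF time in three steps.

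- Rule 2: "Any Hauser diary day on which rescue medication was used will NOT be considered a valid symptom diary day". It adds: "The Hauser diary data reported on that day hereafter referred to as a rescue diary day, will not be used".
- Rule 7: "The daily OFF time for every rescue diary day will be replaced by the subject's baseline OFF time, that is, the baseline 3-day average".
- Rule 8 keeps the day in the visit mean: valid days "and/or rescue diary days will be used to compute the average daily OFF time". At most three days count.

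SAP 3.2 then lists ON time with and without troublesome dyskinesia as secondary diary endpoints and states: "The same algorithm and rules employed for the calculation of OFF time will be used for the secondary variables". Rule 7 names OFF time only. The natural reading of the extension is that each variable takes its own baseline average. The rule runs through Period A, and through Period B for subjects who consented under Amendment 2 before entering it.

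On rescue, Protocol 5.9 says: "Rescue medication is permitted in the form of L-Dopa", with dose and frequency left to the investigator. Dyskinesia has its own secondary objective in Protocol 2.2: "To evaluate the effect of PF-06649751 administered once daily on dyskinesia in subjects with Parkinson's disease".

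**The concern.** Entering baseline means entering zero change. Where the drug is expected to improve the variable, that withholds credit on a rescue day, which is the cautious choice. The same value does different work where the worry is worsening. If a subject records more troublesome dyskinesia than at baseline on a rescue day, the record is set aside and the day counts as unchanged.

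At stake is the diary evidence for a named secondary objective. The size of the effect depends on how often rescue is used in each arm, and a reader of the planned tables could not work it out.

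**Working it through.** **The plan's own figures.** The plan gives none for this endpoint. Its design figures concern OFF time (Protocol 9.1: SD 2.9 h, 32 evaluable per arm). SE = 2.9 × √(2/32) = 0.725 h. C2 needs an observed effect of 1.645 × 0.725 = 1.19 h, so the 1.5 h of C1 is the binding cutoff. The chance of passing is 1 − Φ((1.5 − 2.25)/0.725) = 84.95% at a true effect of 2.25 h and 1 − Φ(1.5/0.725) = 1.93% at zero, matching the stated 85% and 2%. Nothing below depends on them.

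**Step 1: one subject, three diary days.** Let dN and dR be the change from baseline in ON time with troublesome dyskinesia on a non-rescue and a rescue day, and k the number of rescue days.

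- Recorded mean change: ((3 − k)·dN + k·dR)/3
- SAP mean change: (3 − k)·dN/3
- SAP minus recorded: −(k/3)·dR

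The documents give no values for dN or dR. Those below are assumed.

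| dN (h) | dR (h) | k | Recorded (h) | SAP (h) |
|---|---|---|---|---|
| 0.5 | 1.0 | 1 | 0.67 | 0.33 |
| 0.5 | 1.0 | 2 | 0.83 | 0.17 |
| 0.5 | 1.0 | 3 | 1.00 | 0.00 |
| 0.5 | 0 | 1 | 0.33 | 0.33 |
| 0.5 | −0.5 | 1 | 0.17 | 0.33 |

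The SAP value is too low when dR is positive, correct when it is zero, and too high when it is negative. The k = 3 row assumes that rules 7 and 8 govern. Rule 11 could instead set that visit to missing, because such a subject has no valid home diary day.

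**Step 2: the drug-placebo contrast.** Let pA and pP be the shares of diary days with rescue on active and placebo. The SAP contrast minus the recorded contrast is −(pA·dR_A − pP·dR_P). Assume the drug adds 0.50 h, placebo adds 0, and rescue adds x in both arms.

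- Equal shares p: recorded contrast 0.50 h whatever x is. SAP contrast (1 − p) × 0.50, which is 0.475 h at 5% and 0.35 h at 30%.
- Active 30%, placebo 10%, x = 1 h: recorded 0.7 × 0.5 + 0.3 × 1.5 − 0.1 × 1.0 = 0.70 h. SAP 0.7 × 0.5 = 0.35 h, lower.
- Active 10%, placebo 30%, x = 1 h: recorded 0.9 × 0.5 + 0.1 × 1.5 − 0.3 × 1.0 = 0.30 h. SAP 0.9 × 0.5 = 0.45 h, higher.

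**Step 3: is the recorded value shown anywhere?** The sensitivity analyses in SAP 6.1.1.2 cover OFF time only and vary model and population, not the rescue rule. SAP 6.2.1 plans one derivation for this endpoint. SAP 6.5.4 summarises rescue doses by arm and visit, not diary days overwritten. Appendix 1 marks the endpoint OC, which SAP 5.3 describes as observed cases with missing data not imputed. That label does not tell a reader that recorded hours were replaced.

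**The case against.** **OFF time and troublesome dyskinesia point the same way.** A reader might infer that benefit and harm run in opposite directions for the two. They do not. Protocol 7.3.1 groups both as bad time, a fall is benefit for each, and baseline means no change rather than zero hours. If the drug lowers dyskinesia relative to baseline, substitution withholds credit here too, and the monkey data in Protocol 1.3.2 suggest less dyskinesia than with L-Dopa. This stands. However, Protocol 1.3.1 also reports that earlier full D1/D5 agonists caused dyskinesia comparable to L-Dopa, so worsening cannot be assumed away.

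**Rescue days need not be the most dyskinetic days.** A reader might infer that they are, because rescue is L-Dopa. Protocol 1.3.1 links dyskinesia to chronic therapy over years, not to single extra doses, and a rescue day may hold more OFF and less ON time. This stands.

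**Recorded values answer a different question.** They bring dyskinesia caused by rescue into the contrast. Against the assumed drug effect of 0.50 h, the two unequal-rescue scenarios leave the SAP value off by 0.15 h and 0.05 h, and the recorded value off by 0.20 h both times. Recorded values do better when rescue use is equal, or when the target is the effect regardless of rescue. This stands against making them the only version, but not against showing them.

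**Other data cover dyskinesia.** MDS-UPDRS Part IV asks about the past week, has no rescue overwrite (SAP 3.2.2) and is analysed at all visits (SAP 6.2.2). Adverse events are compared by arm. C1 and C2 rest on OFF time. This limits the consequence, but neither source gives diary hours.

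**Conclusion.** The concern holds in a limited form. The rescue rule reaches ON time with troublesome dyskinesia, it erases any worsening recorded on rescue days, and no planned analysis would reveal this. Each rescue day in a three-day mean removes one third of that day's change from baseline.

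The stronger statement that the endpoint understates dyskinesia is not supported. The within-arm change is understated only if rescue-day values exceed baseline. The contrast can err either way, depending on rescue shares and rescue-day change. The documents give neither, so every figure in hours above is an illustration and the real size is unknown. The primary endpoint and its decision criteria are unaffected.

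**What to change.** In SAP 3.2 and 6.2.1, add a pre-specified analysis of ON time with troublesome dyskinesia that uses the recorded diary values on rescue days, under the same requirement of 12 awake hours as any other day. Report it beside the baseline-substituted version. Tabulate by arm and visit the share of diary days overwritten. Leave the choice of primary version to the sponsor as an estimand decision, and state it.

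The same edit can say that each diary variable takes its own baseline average, and settle whether rule 11 or rules 7 and 8 apply when every diary day is a rescue day.

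The cost is one extra derivation and one table, from diaries already collected. In the recorded-value version, the dyskinesia hours need not sum to 24 h with the substituted OFF and good ON time, which a footnote can explain.

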3.2.1. MDS-UPDRS Part III

MDS-UPDRS Part III assesses the motor signs of Parkinson's disease and is administered by the investigator. It is comprised of 33 sub-scores based on 18 items, several with right, left or other body distribution scores. Each question is anchored with five responses that are linked to commonly accepted clinical terms: 0 = normal, 1 = slight, 2 = mild, 3 = moderate, and 4 = severe. Assessments will be done at times specified in the STUDY PROCEDURES section of the protocol. Higher total scores indicate more severe motor signs of Parkinson's disease. There are four subscales:

- The tremor subscale, which is the sum of scores for resting tremor amplitude in five body parts (5 items: right upper extremities, left upper extremities, right lower extremities, left lower extremities, and lip/jaw), postural tremor (2 items) and Kinetic tremor (2 items) in the hands (range 0–36).

If more than 1 item (>20%) is missing for a time point, the subscale score for that time point is missing; otherwise, the subscale score will be imputed as follows: sum of the non-missing items X (total number of items)/ (number of items non-missing).

- The rigidity subscale is the sum of rigidity scores for limbs and neck (5 items, range 0–20).

The subscale score will be missing if more than 1 item (>20%) is missing.

- The bradykinesia subscale is the sum of scores for finger tapping (2 items), hand movements (2 items), pronation and supination movements (2 items), toe tapping (2 items) and Global spontaneity of movement (body bradykinesia) (1 item) (range 0–36).

If more than 1 item (>20%) is missing for a time point, the subscale score for that time point is missing; otherwise, the subscale score will be imputed as follows: sum of the non-missing items X (total number of items)/ (number of items non-missing).

- The PIGD subscale is the sum of gait (1 item), freezing of gait (1 item) and postural stability (1 item) (range 0-12).

The subscale score will be missing if more than 1 item (>20%) is missing.

If more than 7 of the MDS-UPDRS Part III items are missing for a time point,⁵ the part score for that time point is missing; otherwise, the part score will be imputed as follows: sum of the non-missing items X (total number of items)/ (number of items non-missing).

Baseline will be the Day 0 measurement.

3.2.2. MDS-UPDRS Parts I, II, IV, and Total Score

MDS-UPDRS Parts I, II, and IV will be done at times specified in the STUDY PROCEDURES section of the protocol. Each question is anchored with five responses that are linked to commonly accepted clinical terms: 0 = normal, 1 = slight, 2 = mild, 3 = moderate, and 4 = severe. Higher part and total scores indicate more severe signs of Parkinson's disease.

- Part I: Non-Motor Aspects of Experiences of daily Living (nM-EDL); this portion of the scale assesses the non-motor impact of Parkinson's disease on patients' experiences of daily living. There are 13 questions. Part 1A is administered by the rater (six questions) and focuses on complex behaviors. Part 1B is a component of the self-administered Patient Questionnaire that covers seven questions on non-motor experiences of daily living. (range 0-52)

If more than 1 item is missing for a time point,⁵ the part score for that time point is missing; otherwise, the part score will be imputed as follows: $\text{sum of the non-missing items} \times (\text{total number of items}) / (\text{number of items non-missing})$.

- Part II: Motor Aspects of Experiences of Daily Living (M-EDL); this portion of the scale assesses the motor impact of Parkinson's disease on patients' experiences of daily living. There are 13 questions. (range 0-52)

If more than 2 items are missing for a time point,⁵ the part score for that time point is missing; otherwise, the part score will be imputed as follows: $\text{sum of the non-missing items} \times (\text{total number of items}) / (\text{number of items non-missing})$.

- Part IV: Motor Complications; in this section, the rater uses historical and objective information to assess two motor complications, dyskinesias and motor fluctuations that include OFF-state dystonia. Use all information from patient, caregiver, and the examination to answer the six questions that summarize function over the past week including today. (range 0-24)

The part score will be missing if any underlying question is missing.⁵

[figure not shown]
- MDS-UPDRS Total Score: The sum of Parts I, II, III, and IV.

The total scores will be missing if any underlying part score is missing.

Baseline will be the Day 0 measurement.

[figure not shown]
CCI

CCI

[figure not shown]
090177e18f6e873a\Approved\Approved On: 26-Sep-2018 05:14 (GMT)

CCI

090177e18f6e873a\Approved\Approved On: 26-Sep-2018 05:14 (GMT)

CCI

090177e18f6e873a\Approved\Approved On: 26-Sep-2018 05:14 (GMT)

CCI

[figure not shown]
090177e18f6e873a\Approved\Approved On: 26-Sep-2018 05:14 (GMT)

CCI

090177e18f6e873a\Approved\Approved On: 26-Sep-2018 05:14 (GMT)

CCI

3.4. Baseline Variables

Baseline is defined as Day -1 (study derived day and equals to nominal visit Day 0 as noted in the protocol) measurement.

Baseline variables include

- Demographics;
- Medical history;
- Prior/current medication;
- MMSE Total Score;
- Hoehn & Yahr Stage while the subject is ON (if applicable);
- Diary endpoints (OFF time + all other diary measures);
- MDS-UPDRS (Part I, II, III, IV, and Total Score);
- CCI [REDACTED];
- QUIP-RS;
- Primary diagnosis and duration;
- Prescribed L-Dopa dose;
- Background concomitant Parkinson's Disease medications (ATC level classification and a combination of the different classifications);
- Region (stratification factor).

These data will be summarized as part of the baseline characteristics.

The sponsor or designee may verify critical elements of the screening and enrollment process and, in cases where verification is required, will provide written authorization (eg, e-mail) concurring with the investigator assessment that the subject is eligible to return for Day 0 (Randomization) assessments. Eligibility may also be documented via telephone authorization followed by written confirmation. The key elements to be reviewed by the sponsor may include Parkinson's disease diagnosis, MDS-UPDRS scores, concordance testing results, medical history, concomitant medications, and select screening safety assessments including labs, ECGs, and vital signs.

Baseline daily OFF time will be a continuous covariate in the MMRM analysis of the primary analysis (See [Section 5.2.2.1](#)). Geographic region will also be a factor, and defined as North America, Japan, and Europe. The geographic regions are stratification factors for the randomization.

Concomitant and prior medications will be coded using the WHO-drug coding dictionary. In addition, concomitant and prior non-drug treatments/procedures will also be coded using the MedDRA coding dictionary.

3.5. Safety Endpoints

Adverse events, ECGs, blood pressure, pulse rate, C-SSRS, QUIP-RS, PWC-20 and safety laboratory data will be reviewed and summarized on an ongoing basis during the study to evaluate the safety of subjects.

3.5.1. Adverse Events

An adverse event is considered treatment emergent relative to a given treatment if:

- the event occurs for the first time during the effective duration of treatment and was not seen prior to the start of treatment (for example, during the baseline or run-in period), or
- the event was seen prior to the start of treatment but increased in severity during treatment.

The effective duration of treatment is determined by the lag time. Any event occurring within the lag time, whether this occurs during a break in treatment or at the end of treatment, is attributed to the corresponding treatment period. An infinite lag will be used for the study.

A 3-tier approach will be used to summarize AEs. Under this approach, AEs are classified into 1 of 3 tiers. Different analyses will be performed for different tiers (See [Section 6.6.1](#)).

Tier-1 events: These are pre-specified events of clinical importance and are maintained in a list in the product's Safety Review Plan (no Target Medical Events {TMEs} have been defined at this point in time)

Tier-2 events: These are events that are not tier-1 but are "common". A MedDRA PT is defined as a Tier-2 event if there are 4 or more subjects with that PT in any treatment group, given the trial will have less than 400 or fewer subjects per treatment group ("Rule of 4").

Tier-3 events: These are events that are neither Tier-1 nor Tier-2 events. Pfizer standard safety output where all AEs will be included (ie, no new outputs).

Adverse Events will be determined Overall, and separately for Period A and Period B.

3.5.2. Laboratory Data

Laboratory data will be measured at times specified in the STUDY PROCEDURES section of the protocol. Prolactin data collection has the potential to unblind subjects and will be handled blindly by the study team. The Data Blinding Plan will provide details.

Baseline will be the Day 0 measurement.

Determine if there are any laboratory data abnormalities of potential clinical concern as defined in Pfizer Data Standards. This data will be determined Overall, and separately for Period A and Period B.

3.5.3. Vital Signs (Blood Pressure and Pulse Rate)

Blood pressure and pulse rate will be measured at times specified in the STUDY PROCEDURES section of this protocol. Subject temperature must also be assessed at Screening and Day 0 (Randomization) to confirm no symptoms of fever (see Exclusion Criteria #6). Additional collection times, or changes to collection times of blood pressure and pulse rate will be permitted, as necessary, to ensure appropriate collection of safety data.

Orthostatic hypotension is defined as a decrease of ≥ 20 mmHg for systolic blood pressure or ≥ 10 mmHg for diastolic blood pressure 2 minutes after standing from a supine position. Orthostatic hypotension may be symptomatic or asymptomatic.

Baseline will be the Day 0 measurement.

Determine if there is any blood pressure or pulse rate data abnormalities of potential clinical concern as defined in Pfizer Data Standards. This data will be determined Overall, and separately for Period A and Period B.

